## 9 STATISTICAL CONSIDERATIONS

**NOTE: Detailed statistical analysis plan (SAP) will be a separate document**

### 9.1 STATISTICAL METHODS

The primary feasibility outcomes are between-group difference in mean  $UF_{NET}$  rate, protocol adherence, and recruitment rate. The primary objective of this feasibility trial to measure a minimum of 0.53-0.57 mL/kg/h separation in the delivered patient mean  $UF_{NET}$  rates between the restrictive and liberal  $UF_{NET}$  rate groups. We estimated that, if each of the 10 ICUs enrolled a minimum of 0.93 patient per 2 months for 24 months, we would have a total of 111 patients. Using the sample size calculation for SW-CRT design, we estimated that 111 patients will have 80% power at a two-sided alpha of 0.05 to reject the null hypothesis that the average  $UF_{NET}$  rate was at least 0.53-0.57 mL/kg/h different between the two groups, using intra-cluster correlation coefficient of 0.01, at a standard deviation of 0.75, and assuming mean  $UF_{NET}$  rate of 1.0 mL/kg/h (Table 6). After accounting for a very small attrition rate, we plan to recruit from each of the 10 ICUs: 1 patient per 2 months for 24 months for a total of 112 subjects or 56 patients per group.

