3. The patient or surrogate decision-makers decide to withdraw life-sustaining treatment.
4. The patient dies.
5. Day 28 after study enrollment, whichever occurs first.

**Primary Outcomes:** The primary feasibility outcomes are as follows:

1. Between-group separation in mean delivered UFNET rates of a minimum of 0.53 mL/kg/h.
2. Protocol deviation defined as UFNET rate out of range of >0.5 mL/kg/h lower or higher than the assigned UFNET rate range for six consecutive hours.
3. Patient recruitment of one patient per time window per ICU.

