### **Sample Size/Interim Monitoring**

[figure not shown]
1. Using the sample size calculation for SW-CRT design, 111 patients will have 80% power at a two-sided alpha of 0.05 to reject the null hypothesis that the average UFNET rate was at least 0.53 mL/kg/h different between the two groups, using intra-cluster correlation coefficient of 0.01, at a standard deviation of 0.75, and assuming mean UFNET rate of 1.0 mL/kg/h. We will enroll 112 subjects or 56 patients per group.
2. The principal analysis will be intent-to-treat based upon randomization assignment.
3. The trial progress will be evaluated by an independent Data and Safety Monitoring Board (DSMB). Being a feasibility study there will be no interim analyses.

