## 6 STUDY POPULATION AND ENROLLMENT

### 6.1 SETTING

The trial will accrue a maximum of 112 patients. Participants will be enrolled from 5 ICUs at the UPMC, Pittsburgh, PA, and 5 ICUs at the Mayo Clinic, Rochester, MN. At the UPMC, we will include the Transplant ICU, Medical ICU, and the Surgical Trauma ICU at the Presbyterian hospital, and the Medical-surgical ICU and Neuro-ICU (ICU8) at the Mercy hospital. At Mayo Clinic, we will enroll at the Medical-surgical ICU from the Methodist campus, and the Cardiac, Medical, Surgical, and CV Surgery ICUs at St. Mary's campus. No study ICU has a protocolized approach to fluid removal, and instead, clinicians determine the timing and rate of UFNET. All ICUs use specialized ICU nurses trained and certified in delivering CKRT. We expect each ICU to recruit one or more subjects per time window based on annual volume and past enrollment, allowing complete enrollment in 2.0 years.

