### 6.3.2 RANDOMIZATION UNIT

Following best practice recommendations for evaluation of system-level interventions, the unit of randomization is the cluster (*e.g.*, ICU) rather than the individual patient. During the first six months of data collection, all sites will continue with a liberal UFNET rate strategy. Thereafter, one ICU will be randomized to deploy the restrictive UFNET rate strategy every two months or when a maximum of 10 patients have been enrolled, whichever occurs first, and stay in this strategy until the end of the study (Figure 6).

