**Figure 6: Stepped-wedge cluster-randomized trial design**

We will use a computer-generated randomization scheme to determine the order in which each ICU would cross over from the liberal group to the restrictive group, with new crossover occurring every two months or whenever 10 patients have been enrolled, whichever occurs first. This trial design will allow us to stagger the implementation of the restrictive UFNET strategy while maintaining concurrent control over data collection in the ICUs that were not yet using the restrictive UFNET strategy.

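### The 112 patients, 56 per group and 80% power in Protocol 9.1 and Section 4 agree neither with the crossing rule in 6.3.2 nor with the stated accrual rate

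*Protocol*

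**What the plan says.** Protocol 9.1 first supposes that each of the 10 ICUs enrols "a minimum of 0.93 patient per 2 months for 24 months, we would have a total of 111 patients". After an unquantified, very small attrition allowance it plans "1 patient per 2 months for 24 months for a total of 112 subjects or 56 patients per group". Section 4 (Sample Size/Interim Monitoring) repeats: "We will enroll 112 subjects or 56 patients per group". Both places attach 80% power at two-sided 0.05 to 111 patients, with SD 0.75 and ICC 0.01. Table 6 lists a detectable difference of 0.53 mL/kg/h at ICC 0.01 and 0.57 at ICC 0.1.

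The schedule is in 6.3.2: "During the first six months of data collection, all sites will continue with a liberal UF NET rate strategy". ICUs then cross one at a time and do not return, "with new crossover occurring every two months or whenever 10 patients have been enrolled, whichever occurs first". Section 6.1 adds "The trial will accrue a maximum of 112 patients", and expects each ICU to "recruit one or more subjects per time window based on annual volume and past enrollment, allowing complete enrollment in 2.0 years". The recruitment outcome in Section 4 (Primary Outcomes) is "Patient recruitment of one patient per time window per ICU"; 5.8.1 repeats the criterion. The text does not give the length of a time window.

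**The concern.** A stepped wedge has equal group sizes only if its calendar makes half of the ICU-time restrictive. A long all-liberal lead-in followed by slow single-ICU crossings pushes patients into the liberal group, so an even split needs a derivation. Section 9.1 gives none. Separately, the stated rate, number of ICUs and duration do not multiply to the stated total.

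At stake is the expected size of the restrictive group, whose feasibility is the trial's stated objective, and therefore the precision of its adherence and safety estimates. There is also the question of which calendar the power statement describes. The crossing rule is operational, so unclear wording there affects when ICUs actually switch.

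**Working it through.** **Inputs.** 10 ICUs, 24 months, rates 0.93 and 1 per ICU per two months, SD 0.75, ICC 0.01 (9.1); ICC 0.1 (Table 6); six liberal months, then one crossing every two months or at 10 patients (6.3.2); maximum 112 and 2.0 years (6.1). The SAP still describes 144 patients in 6 ICUs and was not used for these figures.

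**Accrual.** ICUs × windows × rate, with 24/2 = 12 windows:
- 10 × 12 × 0.93 = 111.6, which reproduces 111.
- 10 × 12 × 1 = 120, not 112.
- 112/120 = 0.933 per ICU per two months. At 1 per ICU per two months (5 a month in total), 112 is reached at 112/5 = 22.4 months.

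**Reproducing 56:56.** Take one two-month liberal window and ten steps, 11 windows in all. Restrictive cells are 10 + 9 + … + 1 = 55 of 110, so 112 × 55/110 = 56.

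**Split under 6.3.2** (fixed two-month steps, even accrual, N = 112):

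| First crossing | Enrolment | Restrictive ICU-months | Restrictive patients |
|---|---|---|---|
| month 6 | 24 months | 18+16+…+0 = 90 of 240 | 42.0 |
| month 6 | 22.4 months | 16.4+14.4+…+0.4 = 75.6 of 224 | 37.8 |
| month 8 | 24 months | 16+14+…+0 = 72 of 240 | 33.6 |
| month 8 | 22.4 months | 14.4+12.4+…+0.4 = 59.2 of 224 | 29.6 |
| month 6 | 30 months | 24+22+…+6 = 150 of 300 | 56.0 |

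Only the last row reaches 56, and it needs 30 months of enrolment. In the first row the tenth ICU crosses at month 24, when enrolment ends.

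**The 10-patient trigger** (simulated, first crossing at month 6, 112 patients arriving at random):
- Counted across the trial, equal ICU volumes: mean 45.9 restrictive over 24 months and 42.4 over 22.4 months; 56 or more in about 4% and 1% of runs. The trigger adds little because planned accrual is itself 9.3 to 10 patients per two months.
- Counted per ICU, equal volumes: means from 42.9 to 49.7, depending on whose count applies and on duration.
- Counted per ICU, with a 10:1 spread of ICU volumes (an assumption; the documents give no volumes for all ten ICUs): up to 52.0 over 24 months.

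**Power.** Hussey–Hughes variance with categorical time, N = 112, total SD 0.75, ICC 0.01:

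Var = I·s²(s² + Tτ²) / [(IU − W)s² + (U² + ITU − TW − IV)τ²]

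Here I is the number of ICUs, T the number of windows, τ² = 0.01 × 0.5625 = 0.005625 and s² = 0.556875/(patients per cell). U is the number of restrictive cells, W the sum of squared window totals and V the sum of squared ICU totals.
- 11 windows: U = 55, W = V = 385, s² = 0.556875/(112/110) = 0.5469. Var = 5.469 × 0.6088/(90.24 + 5.57) = 0.03475, SE 0.186. Power at 0.53 is Φ(0.53/0.1864 − 1.96) = 81.1%.
- 6.3.2 over 24 months: U = 45, W = V = 285, T = 12, s² = 0.556875/(112/120) = 0.5967. Var = 5.967 × 0.6642/(98.45 + 6.50) = 0.03776, SE 0.194. Power is 77.9%, detectable difference 2.80 × 0.1943 = 0.544.
- 6.3.2 over 22.4 months: power 78.8%, detectable difference 0.538.
- ICC 0.1, difference 0.57: 81.1% for 11 windows, 78.7% for 6.3.2 over 24 months.

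The SAP's main model (4.1) treats time as random. If time variance is 1% to 10% of the total (an assumption), power at 0.53 under 6.3.2 is 91% to 94%.

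**The case against.** The best defence is that 56:56 and 80% power are consistent with each other under the 11-window layout. At 1 patient per ICU-window that layout yields 10 × 11 = 110, close to 112. Figure 6, the design diagram, is not shown in the text available here. The six-month sentence may therefore be the outlier, not the group sizes. This stands, and it rules out simply declaring 56 wrong. It does not remove the conflict: the six months are stated in 6.3.2 and again in Section 3, 9.1 and 6.1 give 24 months, and 11 two-month windows last 22.

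On accrual, 112 can be read as 111 plus one for attrition, with 1 patient a rounded 0.93, and the cap could stop enrolment at 22.4 months, inside 2.0 years. That is a fair account of how the sentence arose, and N itself is not in doubt. The sentence still attaches 112 to a rate and duration that give 120.

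A reader might go further and infer that a fully enrolled trial must fail its own recruitment criterion, since 112/120 = 0.93 is below 1. The documents do not support that. It requires a two-month window, which is not defined, and enrolment filling all 24 months. At 1 per window with a stop at the cap, the criterion is met, and 5.8.1 summarises recruitment per active screening month.

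Nor is an underpowered trial a safe inference. Unequal exposure is ordinary in a stepped wedge, the SAP's model does not need equal groups, and the shortfall is 1 to 2 points with categorical time for a first crossing at month 6.

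**Conclusion.** The inconsistency is real on the text, in both parts. The accrual conflict is plain arithmetic: 120 against 112. For the split, the literal 6.3.2 schedule gives about 42:70, 14 fewer restrictive patients than stated. That figure assumes fixed steps, a first crossing at month 6 and even accrual over 24 months. Across the readings tried the expected restrictive count runs from about 30 to about 52, so a single narrow shortfall should not be quoted. An individual trial could still reach 56 by chance. What can be said firmly is that no reading tried within 24 months averages 56, and that the stated split and power match one two-month liberal window plus ten steps. Power under 6.3.2 is about 78% to 79% instead of 80% at 0.53 with categorical time, for a first crossing at month 6, and there may be no loss with random time. This should be corrected, but it does not threaten the trial.

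**What to change.** Reconcile 6.3.2 and Figure 6 with 9.1 and Section 4, in one of two ways:
- If 6.3.2 is the design, replace the even split with the expected split under that rule. State the accrual, duration and ICU-volume assumptions and the range. Restate the power or detectable difference, and name the time model.
- If the 11-window layout is the design, keep 56 per group and correct the six-month text (6.3.2, Section 3) and the 24-month text to match it.

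In either case, say whether the 10 patients are counted across the trial or per ICU, and when the first crossing falls. Make rate, duration and total agree: for example 0.93 per ICU per two months over 24 months, or 1 per ICU per two months with the cap reached at about 22.4 months. Define the time window so that full enrolment of 112 is compatible with the criterion of 1 patient per ICU per window.

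The cost is wording in a few sections and one short recalculation. No extra patients are needed.

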**Table 6: Detectable difference in mean  $UF_{NET}$  rates**

Difference	ICC	Alpha	Power	N
0.53	0.01	two-sided	0.8	111
0.57	0.1	two-sided	0.8	111
0.57	0.01	one-sided	0.8	126
0.63	0.1	one-sided	0.8	126

*ICC, intra-cluster correlation coefficient*

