### 3.6 SAMPLE SIZE AND MONITORING

1. Using the sample size calculation for stepped wedge cluster randomized trial (SW-CRT) design, 126 patients will have 80% power at a two-sided alpha of 0.05 to reject the null hypothesis that the average  $UF_{NET}$  rate was at least 0.52 mL/kg/h different between the two groups, using intra-cluster correlation coefficient of 0.01, at a standard deviation of 0.75, and assuming mean  $UF_{NET}$  rate of 1.0 mL/kg/h. After accounting for a potential 10% attrition rate, the sample size was increased to 144 subjects or 72 patients per group.
2. The principal analysis will be intent-to-treat based upon randomization assignment.
3. The trial progress will be evaluated by an independent Data and Safety Monitoring Board (DSMB). Being a feasibility study there will be no interim analyses.

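### Protocol Table 6: the one-sided rows cannot be right as labelled, and the two-sided rows reproduce with one baseline window, not the six-month baseline the protocol describes

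*Protocol*

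**What the plan says.** Protocol 9.1 states that "111 patients will have 80% power at a two-sided alpha of 0.05 to reject the null hypothesis" concerning the separation in mean delivered UFNET rate, "using intra-cluster correlation coefficient of 0.01, at a standard deviation of 0.75". It gives the difference as a range: "rate was at least 0.53-0.57 mL/kg/h different between the two groups". Table 6 ("Detectable difference in mean" rates) has four rows, with columns for difference, ICC, sidedness, power and N:

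- "0.53 0.01 two-sided 0.8 111"
- "0.57 0.1 two-sided 0.8 111"
- "0.57 0.01 one-sided 0.8 126"
- a fourth row: 0.63, ICC 0.1, one-sided, 0.8, 126

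The table gives no alpha level, number of ICUs or number of windows for any row.

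On the schedule, Protocol 6.3.2 has all ICUs on the liberal strategy for the first six months. One ICU then crosses every two months, or once 10 patients are enrolled if that comes first. Protocol 9.1 assumes 10 ICUs, 0.93 patient per ICU per two months and 24 months, and plans 112 patients, 56 per group. Protocol 6.1 caps enrolment at 112.

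SAP 3.6 still describes the earlier size: "126 patients will have 80% power at a two-sided alpha of 0.05", for a difference of 0.52 at ICC 0.01. Its trial summary (section 3) has 6 ICUs.

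**The concern.** With the design, ICC, SD, power and alpha level held fixed, more patients and a one-sided test each reduce the detectable difference. Table 6 shows the opposite at both ICCs, so a reader can see from the table alone that two of its four rows are wrong as labelled.

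Two further mismatches affect the rows that the plan does use. The text of 9.1 puts 0.57 under ICC 0.01, where Table 6 has only 0.53 for a two-sided test. An equal split between groups also fits a stepped wedge with a single baseline window. Three all-liberal windows out of 12 shift the allocation towards the liberal strategy and cost power. What is at stake is the stated 80% power and 56 per group for the first primary feasibility outcome.

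**Working it through.** **Inputs.** SD 0.75 (taken as the total SD), ICC 0.01 or 0.1, power 80%, two-sided alpha 0.05, N = 111, 10 ICUs (Protocol 9.1); schedule from Protocol 6.3.2; 6 ICUs and N = 126 from SAP 3 and 3.6.

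**Formula.** Hussey–Hughes variance with fixed period effects and a random ICU intercept. I is the number of ICUs, T the number of windows, m = N/(I·T), τ² = 0.75²·ICC and σ² = 0.75²·(1 − ICC)/m. U is the number of restrictive ICU-windows, W the sum over windows of the squared number of restrictive ICUs, and V the sum over ICUs of the squared number of restrictive windows.

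Var = I·σ²(σ² + Tτ²) / [(I·U − W)σ² + (U² + I·T·U − T·W − I·V)τ²]

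Detectable difference = SE × (z_alpha + z_power). The multiplier is 1.960 + 0.842 = 2.802 for two-sided 0.05 and 1.645 + 0.842 = 2.486 for one-sided 0.05.

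**1. Reproducing the two-sided rows.** Take 10 ICUs, 11 equal windows, one baseline window and one crossing per window, so U = 55 and W = V = 385. At N = 111 and ICC 0.01, σ² = 0.5519 and τ² = 0.005625.

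- Numerator: 10 × 0.5519 × (0.5519 + 0.0619) = 3.387
- Denominator: 165 × 0.5519 + 990 × 0.005625 = 96.63
- Variance 0.03505, SE 0.1872, detectable difference 0.525

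At ICC 0.1 the SE is 0.2015 and the difference 0.564. With exactly one patient per cell (N = 110) the values are 0.527 and 0.567, which round to the printed 0.53 and 0.57. The design has 55 of 110 cells restrictive, which is the 50:50 split behind 56 per group.

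**2. One-sided rows, without assuming a layout.** At one-sided 0.05 the multiplier falls by the ratio 2.486/2.802 = 0.888. Before counting the 15 extra patients, rows 3 and 4 should be no larger than 0.888 × 0.53 = 0.47 and 0.888 × 0.57 = 0.51.

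**3. One-sided rows, by layout, N = 126:**

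| Layout | ICC 0.01 | ICC 0.1 |
|---|---|---|
| 10 ICUs, 11 windows | 0.438 | 0.475 |
| 10 ICUs, 12 windows, 3 baseline | 0.457 | 0.489 |
| 10 ICUs, 13 windows, 3 baseline | 0.474 | 0.502 |
| 6 ICUs, 7 windows | 0.461 | 0.505 |
| Printed in Table 6 | 0.57 | 0.63 |

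Reading 0.75 as a within-ICU SD gives 0.440–0.477 and 0.500–0.533, still well below the printed values. One-sided 0.025 (total SD) gives 0.494–0.535 and 0.535–0.570, which does not match either. Among the combinations tried, only 6 ICUs × 7 windows at one-sided 0.0125 returns both printed values (0.572 and 0.627). The same layout at two-sided 0.05 and ICC 0.01 gives 0.520, the SAP's figure.

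**4. Two-sided rows under the stated schedule.** Six months is three windows. With the first crossing at month 6, the tenth falls at 6 + 9 × 2 = month 24.

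*24 months (12 windows).* The tenth ICU has no restrictive window, so U = 9 + 8 + … + 1 + 0 = 45 of 120 cells, or 45/120 × 111 ≈ 42 patients. W = V = 285. At ICC 0.01, σ² = 0.6020:

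- Variance: 10 × 0.6020 × (0.6020 + 0.0675) / (165 × 0.6020 + 1155 × 0.005625) = 4.031/105.83 = 0.03809
- SE 0.1952, detectable difference 0.547
- Power at 0.53: Φ(0.53/0.1952 − 1.960) = 77.5%

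At ICC 0.1 the SE is 0.2076, the difference 0.582, and power at 0.57 is 78.4%.

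*26 months (13 windows, so that all ten ICUs have a restrictive window).* U = 55 of 130 cells, or 47 of 111 patients. The SEs are 0.2028 and 0.2136 and the detectable differences 0.568 and 0.598. Power is 74.3% at 0.53 (ICC 0.01) and 76.1% at 0.57 (ICC 0.1).

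The N needed for 80% power is 119 and 117 over 24 months, or 129 and 125 over 26 months. The cap is 112.

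**The case against.** Several points on the other side are sound.

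- **Layout.** No section states the number of windows behind Table 6, and Figure 6 is not shown. The 11-window layout is inferred from the numerical match. The schedule itself is not unique either, because the 10-patient trigger could shorten steps.
- **Enrolment.** One patient per ICU per window for 24 months would be 10 × 12 = 120 patients, with power of 80.5% and 81.1%. That exceeds the maximum of 112, so it does not rescue the claim.
- **Analysis model.** SAP 4.1 treats time as random in the main analysis and adjusts for baseline covariates. With random period effects in the 12-window layout at ICC 0.01, power at 0.53 is roughly 89% to 95% for assumed period variances between 0.05 and 0. The documents give no such variance, and as it grows the result returns to the fixed-period value. SAP 4.2.1 also tests a null of a separation below 0.52, which is a different hypothesis from the zero difference behind these power figures. Any single replacement figure therefore depends on the model named.
- **Consequence.** The one-sided rows are used nowhere else, and Protocol 5.8.1 also supports the threshold by a clinical argument around 0.5 mL/kg/h.

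A reader might infer that power falls to about 72% at ICC 0.1. The documents do not support that comparison. It takes the 0.53 of the ICC 0.01 row and applies the ICC of the other row, whereas Table 6 claims 80% at ICC 0.1 only for 0.57. Even the layout that reproduces Table 6 gives only 74.9% for that mixed pair. The like-for-like figure is 78.4%.

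A reader might also take the carry-over from the 6-ICU design as established. It is an inference from matching numbers, and the error in the rows does not depend on it.

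**Conclusion.** The concern stands in two parts of different strength.

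The first is firm. The one-sided rows are wrong as labelled, by about 0.10 to 0.13 mL/kg/h at ICC 0.01 (0.57 against 0.438–0.474) and 0.12 to 0.16 at ICC 0.1 (0.63 against 0.475–0.505), taking one-sided 0.05. The range 0.53–0.57 in Protocol 9.1 is likewise wrongly tied to ICC 0.01 alone.

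The second is moderate and conditional. The stated schedule does not deliver the stated 80% power or 56 per group. Power at 0.53 and ICC 0.01 is about 74–78%, and at 0.57 and ICC 0.1 about 76–78%, with roughly 42 (24 months) or 47 (26 months) of 111 patients restrictive. This rests on fixed period effects, SD 0.75 as the total SD, equal enrolment per ICU-window, and crossings every two months from month 6. The shortfall is about 2 points over 24 months and 4 to 6 over 26 months. It does not undermine a feasibility trial, but the protocol should not print figures that its own design does not give.

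**What to change.** 1. Delete the one-sided rows of Table 6 or recompute them.
2. For every row, state the number of ICUs, number of windows, baseline length, alpha level and N.
3. In Protocol 9.1, tie 0.53 to ICC 0.01 and 0.57 to ICC 0.1 instead of giving one range under ICC 0.01.
4. Recompute the two-sided rows for the actual crossover schedule, say whether the trial runs 24 or 26 months, and restate power and expected group sizes. Under fixed period effects, expect about 74–78% at 0.53 (ICC 0.01) and 76–78% at 0.57 (ICC 0.1). Name the analysis model assumed, because SAP 4.1 specifies random time in the main analysis.
5. Align SAP 3.6 with the 10-ICU design.

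The cost is a text amendment and a slightly less favourable stated power.

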## 10 DATA COLLECTION AND SITE MONITORING

### 10.1 DATA COLLECTION

At the UPMC and the Mayo Clinic, the research staff will collect data and record it either on paper data sheets and/or enter in a secure web database. Once daily, coordinators will enter data that can be analyzed for consistency.

In this trial, we will define protocol deviation as delivered  $UF_{NET}$  rate that lies  $>0.5$  mL/kg/h outside of the target  $UF_{NET}$  rate range in the assigned treatment group for greater than six consecutive hours during fluid removal *without* significant changes in MAP (*i.e.*, MAP  $<65$  mmHg or  $\geq 90$  mmHg). As such, out of range,  $UF_{NET}$  rates  $>0.5$  mL/kg/h beyond the target  $UF_{NET}$  rate range in the assigned treatment group will not constitute a protocol deviation when the bedside team titrated the  $UF_{NET}$  rate as required to manage the patient hemodynamics (*i.e.*, when clinicians appropriately decreased rate or stopped  $UF_{NET}$  for MAP  $<65$  mm Hg or increased rate for MAP  $\geq 90$  mm Hg).

We will also calculate “%on target” value for each center for each of the monitored variables (# of dates on-target for a specific variable/# of opportunities to be on-target for that specific variable). Principle Investigators at each site will receive monthly reports of (1) % on-target for each of the specific variables in the most recent month; (2) % on-target for each of the variables since the beginning of a trial; and (3) a list of dates/times from the past month, the specific data that were entered for those dates/times, and determinations of on- or off-target.

Investigators will use these reports to identify aspects of protocol management that can be improved at their sites. The on-target performances of all ICUs will also be included, allowing investigators at each center to know how their ICU is performing related to other ICUs. On-target performances will be discussed during regular meetings of the Steering Committee.

